Control of Aedes breeding sites with a dual-action insecticidal coating is effective in reducing Dengue transmission: Cluster-randomised Controlled Trial Study

Statistical Analysis Plan

Ubication of study: Metropolitan Area of Cucuta, Colombia

Approval of the protocol: 11 March 2019

Statistical Analysis Plan

Study design and sample size

This is design study for a large cluster randomized trial on the impact of treating water containers with a protective paint. The sample size was calculated for detection of a 50% reduction in the House Index with > 99% power at 5% significance level. Given a baseline HI of 30%, an intra-cluster correlation coefficient (ICC) of 0.01 and a cluster size of 2,000 households it was found that a minimum of 12 clusters per study arm was needed [1]. The same result but with a lower power (68%) was found for a baseline DZC incidence of 3% and a 50% reduction in the intervention arm. A large number of households per cluster was needed as *Ae. aegypti* vectors are day-biters [2] and it was assumed that many household members stay within their neighbourhoods during the day (mainly housewives, small children and school children when the school is close to their house) where they are at risk to get infected. All estimations were done through The Shiny CRT Calculator which is a web-based app to determine sample size and power for cluster trials [3,4].

Data management and analysis

Descriptive analyse and double data entry was practiced (to minimize data entry errors) into a database using Microsoft Office Excel software by an assistant and supervised by the research team. The analysis was done using SPSS software version 28.0.1.1.

Socio-demographic data were entered in a database. We assessed the frequency of variables potentially associated with the outcomes of recent dengue virus infection (sex, age, educational level, peoples` mobility) and selfreported dengue fever in household members (5). Persons' Chi-square test (χ^2) was applied to determine the differences between population characteristics and DZC selfreported cases, and peoples` mobility across all settings. All statistical analyses were performed at a 0.05 significance level.

Entomological indices were analysed per cluster and overall to show the presence, distribution and abundance of *Ae. aegypti* and the breeding sites most productive for adult mosquitoes were identified [6].

House index (HI): Percentage of houses infested with larvae and/or pupae.

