Container index (CI): Percentage of water-holding containers infested with larvae or pupae.

Breteau index (BI): Number of positive containers per 100 houses inspected.

Pupae per person (PPI): Number of pupae per person in each household. To estimate the pupal count for large container (more than 20 L) the methodology by Romero-Vivas [7] was used: According to water level, the number of pupae found was multiplied by a calibration factor.

For the before-after comparison and intervention vs. control arm the difference-in-differences (DiD) approach was applied, taking into account the clustering effect, and estimating the statistical significance through the P-value. Likewise, the reduction of dengue cases reported by SIVIGILA was estimated, according to the annual dengue incidence in intervention and control clusters [8]

Ethical considerations

The household questionnaire was only applied to adults who provided information related to the purpose of this study. No child or adolescent below the age of 18 was interviewed in this study. All people participating in the study were informed in local language through the study information sheet in a written and oral way. They were asked to sign the informed consent form. All participants were informed that their participation was voluntary and that their responses remained anonymous, therefore the study used numbers which replaced the names of individuals and codes which replaced the address of house. Before examining the domestic and peri-domestic water-holding containers, the field team requested permission to enter the house, did the inspection and collected entomological and sociodemographic data.

The study received approval from local health authorities in Cucuta and Norte de Santander and the study protocol was approved by the ethical committee of the Albert-Ludwigs-Universität (application number 141/19) in Freiburg, Germany

References

Article PubMed PubMed Central Google Scholar

1. DANE. Censo Nacional de Población y vivienda 2018. <https://geoportal.dane.gov.co/geovisores/sociedad/cnpy-2018/>. Accessed 30 Apr 2021.

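### The SAP names no primary outcome or multiplicity rule, so up to five arm comparisons at 0.05 carry an overall false-positive chance above 5%

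*SAP*

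**What the plan says.** The SAP's section on data management and analysis defines four indices: House Index (HI), Container Index (CI), Breteau Index (BI) and pupae per person (PPI). For the comparison of arms it says: "For the before-after comparison and intervention vs. control arm the difference-in-differences (DiD) approach was applied", allowing for clustering and judged by a P-value. It does not say which indices this covers. It then adds that "the reduction of dengue cases reported by SIVIGILA was estimated, according to the annual dengue incidence in intervention and control clusters".

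The only statement on error control is "All statistical analyses were performed at a 0.05 significance level". It closes the paragraph on chi-square tests of the survey data, but its wording covers every analysis.

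On sizing, both documents state: "The sample size was calculated for detection of a 50% reduction in the House Index", "with > 99% power at 5% significance level". The same paragraph gives a second target, a halving of a 3% incidence of dengue, Zika or chikungunya (DZC), with 68% power. The SAP title says that the coating "is effective in reducing Dengue transmission". Neither document uses the term primary outcome, orders the outcomes, gives a multiplicity rule or says what result would make the trial positive.

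**The concern.** The sample size points to HI and the title points to dengue. The analysis section treats HI, CI, BI and PPI alike and adds notified dengue. An analyst who follows the SAP could call the coating effective on whichever of these falls below 0.05, and nothing in the plan would forbid it. The stated 0.05 then applies to each test and not to the trial's conclusion.

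There is also a question of what the conclusion is about. A significant fall in CI or BI alone is evidence about breeding sites. Under the present text it could be reported beneath a title that claims reduced dengue transmission.

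**Working it through.** **Inputs from the documents** (SAP, Study design and sample size; Data management and analysis)
- Level 0.05 for every analysis; sidedness not stated.
- "Given a baseline HI of 30%, an intra-cluster correlation coefficient (ICC) of 0.01 and a cluster size of 2,000 households"; 12 clusters per arm; HI 30% to 15%; DZC incidence 3% to 1.5%.
- Candidate outcomes: HI, CI, BI, PPI, and dengue incidence from SIVIGILA (the national surveillance system).

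**Assumptions**
- The correlation between test statistics is not given. I use 0 to 0.95.
- Each test is taken to have exactly its nominal level.

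**Step 1: reproduce the plan's power, and infer sidedness**
- Design effect = 1 + (2,000 − 1) × 0.01 = 20.99.
- Effective sample size per arm = 12 × 2,000 / 20.99 = 1,143.4.
- HI, 30% v 15%, two-sided 0.05: power above 99.9% (plan: above 99%).
- DZC, 3% v 1.5%, two-sided 0.05: power 67.7% (plan: 68%). One-sided 0.05 gives 78.1%.

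The plan's figures reproduce. At the stated cluster size the 68% fits two-sided testing, so I use two-sided 0.05, which is 0.025 in the favourable direction.

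**Step 2: independent tests**
- Any false significant difference, k tests: 1 − 0.95^k. Five tests: 22.6%. Four: 18.5%. Two: 9.75%.
- A false result favouring the coating: 1 − 0.975^k. Five tests: 11.9%. Four: 9.6%. Two: 4.9%.
- Whatever the correlation, five tests cannot exceed 5 × 0.025 = 12.5% in the favourable direction.

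**Step 3: correlated tests** (multivariate normal test statistics, 1,000,000 draws; either direction / favouring the coating)

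| Index correlation | Four indices plus independent dengue | All five equally correlated | Four indices only |
|---|---|---|---|
| 0.5 | 19.8% / 10.1% | 18.3% / 9.1% | 15.6% / 7.8% |
| 0.7 | 17.4% / 8.9% | 14.9% / 7.4% | 13.1% / 6.6% |
| 0.9 | 13.9% / 7.1% | 10.2% / 5.1% | 9.4% / 4.7% |
| 0.95 | 12.6% / 6.4% | 8.4% / 4.2% | 8.0% / 4.0% |

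HI, CI and BI come from the same container inspections, so high correlation among them is plausible. Dengue comes from case notification, so a lower correlation with the indices is plausible. The documents settle neither.

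**Step 4: one named primary, or a fixed sequence**
The chance of any false claim is at most 5% in either direction and 2.5% in favour of the coating.

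**Step 5: what gating dengue behind HI would cost**
The Protocol's sampling section surveys 250 houses per cluster, so the HI test rests on 250 and not 2,000.
- ICC 0.01 (planned): design effect 1 + 249 × 0.01 = 3.49; effective size 3,000 / 3.49 = 859.6; HI power above 99.9%.
- ICC 0.05 (assumed): design effect 13.45; effective size 223.0; power about 97%.
- ICC 0.1 (assumed): design effect 25.9; effective size 115.8; power about 78% with pooled variance and 79% with unpooled.

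**The case against.** **HI may already be primary in effect.** The sample size was calculated for HI, and DZC incidence follows as a check at lower power. This is real evidence of intent, and it is why the fix puts HI first. It is still not a designation: the same paragraph carries a second target, and the title's claim is about something HI does not measure.

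**The number of tests is not stated.** The SAP does not list the indices that receive difference-in-differences. It says dengue reduction was estimated, with no test named, and part of its purpose for the indices is descriptive. This stands, so five is an upper count. With four tests, the either-direction figure runs from 18.5% under independence to 9.4% at correlation 0.9. With only HI and dengue it is 9.75% under independence.

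**The 0.05 sentence sets no success rule.** This also stands. That any one positive outcome would support effectiveness is an inference from the plan's silence.

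**A tempting stronger reading** is that the chance of wrongly declaring the coating effective is 14 to 23%. The documents do not support it. Those figures count false differences in either direction, including against the coating. Under two-sided testing the favourable-direction chance cannot exceed 12.5%, and its comparator is 2.5%, not 5%. Nor is 14% a floor, as the correlated results show.

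**Conclusion.** The concern holds in this form. The plan has no primary outcome, hierarchy, multiplicity rule or definition of success, and it applies 0.05 to every analysis. With up to five two-sided tests, the chance of at least one false significant difference in either direction is at most 22.6% under the correlation structures examined. It is 13.9% at index correlation 0.9 with dengue independent, and about 10% if all five correlate at 0.9. The chance of a false result favouring the coating is up to about 12%, and about 7% at index correlation 0.9 with dengue independent, against 2.5% for a single test.

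These sizes rest on assumed correlations, on two-sided testing inferred from the reproduced 68% power, and on the inference that all the listed outcomes are tested. No plausible choice among these brings the overall rate back to that of a single test unless only one outcome is tested. The documents do not show that anyone intended to claim success on CI or BI alone; they only leave it open.

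**What to change.** In the SAP:
1. Name HI as the single primary outcome, tested at two-sided 0.05.
2. Test SIVIGILA dengue incidence second, at two-sided 0.05, and only if HI is significant. State the test.
3. Report CI, BI and PPI as supportive estimates with 95% confidence intervals and no claim of effectiveness.
4. Allow a conclusion about dengue transmission only if the dengue step is passed.

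Other orderings would also control the error. This one follows the outcome on which the trial was sized.

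The cost is that CI, BI and PPI can no longer carry a claim alone, and dengue cannot be claimed if HI fails. Gating takes almost no power from dengue at the planned ICC of 0.01, but more if clustering is stronger: with 250 surveyed houses per cluster, HI power is about 97% at an assumed ICC of 0.05 and 78 to 79% at 0.1. The dengue step stays weakly powered in any case; the plan's own figure for DZC incidence is 68%.

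The SAP is written in the past tense, so the analysis may already be done. In that case a hierarchy added now is post hoc. The report should say that it was not prespecified, show all the outcomes, and not rest a dengue-transmission claim on an entomological index alone.
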